#### 4.4.11 Magnetic Resonance Imaging

Magnetic resonance imaging of the parotid glands will be performed once during Screening Stage II and again on Day 56. Measurements will be checked for changes during the study, which will be compared with changes in inflammatory and functional parameters of the parotid glands. The MRI scans will be performed in the Diagnostic Radiology Department at the NIH Clinical Center. If the subject is unable to have an MRI for clinical safety reasons, she may still participate in all other aspects of this protocol. . If the baseline measurements are not informative for the study as deemed by the PI, comparable readings at Day 56 will not be performed.

A 3 Tesla magnet will be used for the MRI scans, which will include the following pulse sequences:

- 1. Axial T1-weighted with fat suppression
- 2. Axial T1-weighted without fat suppression
- 3. Axial T2-weighted with fat suppression (short T1 inversion recovery)
- 4. Diffusion-weighted imaging with apparent diffusion coefficient (ADC) maps
- 5. Repeat of techniques #1 and # 2 after intravenous administration of contrast

The signal intensity of the parotid glands will be assessed on the T1- and the T2-weighted scans before and after contrast. To normalize the signal intensity values of the glands, the values will be compared with the signal intensity values of a normal structure not affected by the treatment, i.e., the masseter muscle. In addition, the values of diffusivity in the ADC maps will be measured. A urine or serum pregnancy test must be done within 24 hours prior to the procedure , as applicable. This procedure can take up to 2 hours to complete.

## 4.4.12 Parotid Treatment Irrigation of the parotid duct (dexamethasone or saline)

Treatment irrigation will follow saliva collection on Days 0 and 28. Subjects will be randomized to receive dexamethasone irrigation in either the left or right parotid gland, with placebo (normal saline) administered in the opposite gland. Both the subject and the assessor of salivary flow will be blinded as to which parotid gland receives which treatment. Randomization of parotid glands within subjects will be done by the Pharmaceutical Development Service Department of the Pharmacy at the NIH. The person assessing salivary flow will not be involved in performing the irrigation.

Information on the dexamethasone formulation used in the study is provided in the dexamethasone package insert in Appendix 24.5. The Clinical Center Intravenous Admixture Unit at the NIH will prepare vials containing placebo or dexamethasone. The placebo vial will contain 0.9% sodium chloride for injection. The dexamethasone vial will contain 2 mg of dexamethasone sodium phosphate for injection diluted with 0.9% sodium chloride for injection. Solution will be drawn from the vial into a 1 mL syringe. The volume of each irrigation syringe will be determined by the parotid gland filling volume and specified in the medication order. The total volume will be between 0.5 and 1 mL. All vials will be labeled with the following information:

- Dexamethasone or saline.
- Subject name.
- Subject study number.
- Date dispensed.
- The words "Right parotid" or "Left parotid".
- Dose (2 mg).
- Volume.

Dexamethasone and saline placebo will be dispensed by designated Pharmacy Department staff according to their SOPs. The Pharmacy Department staff will document receipt and dispensation of study drug on drug accountability logs. The dispensation records will identify the name, lot number, and expiration date of the drug, as well as the identification number of subject and the quantity of drug dispensed to each subject. Accidental or intentional destruction of study drug will also be documented. All records will be available for inspection by the clinical trial monitor. Unused study drug will be discarded in the clinic post-procedure per standard NIH drug destruction policy.

The duct system of each gland will be irrigated with the assigned treatment solution (dexamethasone 2 mg or normal saline). For subjects with a fill volume  $\geq 1$  mL, Dexamethasone (2 mg/mL) 1mL will be administered. For subjects with a fill volume <1 mL, the concentration of dexamethasone will be adjusted to administer a total dose of 2 mg. Irrigation will be performed by inserting a 1-mm-caliber catheter filled with the appropriate solution 1 to 2 cm into Stensen's duct. For subjects with a fill volume  $\geq 1$  mL, a 5-mL syringe will be filled with the dexamethasone or saline solution before insertion; the catheter will be connected to the syringe and the solution slowly instilled into to parotid. The catheter will be left in place for 2 minutes of irrigation and then removed. High-speed suction will be used to collect the solution as it runs out. For subjects with a fill volume <1 mL, the dexamethasone or saline will be dispensed in a 1-mL syringe. A urine or serum pregnancy test must be done within 24 hours prior to irrigation, as applicable. This procedure takes up to 30 minutes to complete.

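### Does the vial labelling in Protocol Section 4.4.12 undo the double blind?

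*Protocol*

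**What the plan says.** Section 4.4.12 covers blinding, preparation, labelling and irrigation.

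- **Blinded roles.** "Both the subject and the assessor of salivary flow will be blinded as to which parotid gland receives which treatment". It adds: "The person assessing salivary flow will not be involved in performing the irrigation". The irrigator and the adverse-event evaluator are not mentioned.
- **Labels.** "All vials will be labeled with the following information". The items are the content ("dexamethasone or saline"), subject name and number, dispensing date, right or left parotid, a 2 mg dose, and volume.
- **Drawing up.** After describing vial preparation, the section says: "Solution will be drawn from the vial into a 1 mL syringe". Later it says that for a fill volume of 1 mL or more "a 5-mL syringe will be filled with the dexamethasone or saline solution before insertion", and that below 1 mL "the dexamethasone or saline will be dispensed in a 1-mL syringe". It does not say who fills the syringe.
- **Disposal.** "Unused study drug will be discarded in the clinic post-procedure per standard NIH drug destruction policy".

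Elsewhere, the Précis and Section 4.1 call the trial double-blind. Section 4.4.15 has subjects told their assignment only after the analysis is finished and the investigators are unblinded. Section 8 allows emergency unblinding when it is needed to treat a serious adverse event.

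**The concern.** Two features look wrong on a first reading. A label item that names both products joined by an or could be a blank to fill in with the actual product. The blinding sentence lists two roles and stops, leaving out the person who holds the syringe and the person who judges adverse events.

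The within-subject design raises the stakes. Each subject has one gland on each treatment, so a single openly labelled vial would reveal both assignments. Localized safety against placebo is a secondary objective (Section 2.2), and Section 9.2 counts treatment-related adverse events with the side recorded. Both glands undergo the same procedure and only one receives dexamethasone, so an evaluator who knew the side might attribute a right-sided swelling differently from a left-sided one. In Section 15.3, three of the five alert criteria turn solely on relation to study drug. An irrigator who knew the contents might also instil or retain the two solutions differently. Open labels in the clinic would contradict Sections 4.1, 4.4.15 and 8.

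**Working it through.** No figure in the protocol depends on this point, so the check is a comparison of texts.

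**1. Which label reading fits?**

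| Text | Masked phrase on all vials | Actual content on each vial |
|---|---|---|
| 2 mg dose listed for every vial (4.4.12) | Fits | Does not fit: the placebo vial holds only 0.9% sodium chloride |
| Side item, resolved to right or left per vial (4.4.12) | Neutral | Some support, by parallel form |
| Double-blind (Précis, 4.1) | Fits | Conflicts if clinic staff see the vial |
| Investigators unblinded after analysis (4.4.15) | Fits | Conflicts if an investigator sees the vial |
| Emergency unblinding (8) | Fits | Largely redundant if clinic staff see the vial |

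The dose line weighs most. The parallel form of the side item does not explain why saline should carry a milligram dose.

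**2. Does separating assessor and irrigator imply open vials?** It need not. Section 7.4 lists unpleasant taste, mucosal irritation and pain as possible local effects. Someone present at irrigation could notice these even with masked vials, so the separation is a sensible safeguard under either reading.

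**3. Who judges adverse events?** Section 8 gives follow-up decisions to the medically responsible investigator, and Section 17 gives relatedness of serious events to the principal investigator in consultation with the Clinical Director. Section 4.4.15 treats investigators as blinded until after analysis. The role left without an explicit or implied blind is an irrigator who is not an investigator.

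**4. What could an open label affect?**

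- *Primary endpoint.* Flow is measured by a blinded person who does not irrigate, so measurement is protected under either reading.
- *Events not confined to one side.* Every subject receives dexamethasone in one gland, so knowing which gland adds nothing to attribution.
- *Alert criteria.* They count events or subjects and prompt a notice to the monitoring committee chair; none compares glands. The three that rest on drug relation are not confined to local events. The other two include procedure-related events.
- *One-sided events.* Only here could knowledge of side steer a judgement. The side itself is recorded fact. The protocol uses the word treatment for saline as well (the title of 4.4.12, and 10.1.5), so relation to treatment need not mean relation to dexamethasone. Serious events also get a medical-monitor review (Section 8).

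**5. Do counts help?** The planned preparations are 16 subjects × 2 sessions × 2 glands = 64. That counts preparations, not exposures or bias. Under masked labels, or if the pharmacy fills every syringe, openly labelled vials handled in the clinic number 0. Nor is 64 a strict ceiling, since Section 10.2 allows replacement and Sections 4.3 and 6.2 allow re-screening after a first treatment. The expectation in Section 4.4.6 that most fill volumes are below 1 mL bounds nothing.

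**6. The syringe text.** The preparation paragraph mentions only a 1 mL syringe, while the irrigation paragraph uses a 5 mL syringe for the larger fill volumes. These statements differ and must be reconciled in the working instructions. The choice depends on fill volume and is the same for both solutions, so syringe size does not reveal the assignment.

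**The case for a change.** The best case for a change is that the label should not need interpretation. Where the list means literal words, as with the side, it says so; the content item has no such marker and reads like the blank fields around it. No sentence states that the vials are masked, that the irrigator is blind, or who fills the syringe. Unused drug is discarded in the clinic, so some containers reach it. Protecting the flow measurement does not protect delivery, because the irrigator controls catheter placement, speed of instillation and the 2-minute retention. The remedy would be cheap: a label template and a few sentences.

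Much of this stands as description. The label wording allows two readings, the role list is short, and the syringe sentences differ. What does not follow is that the plan, carried out as written, breaks the blind. Disposal in the clinic fits syringes as well as vials, and the drawing-up sentence sits within the account of pharmacy preparation. The delivery argument holds only if the irrigator actually sees an open label. Dispensing is left to pharmacy procedures, where exact label text would ordinarily be fixed.

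**Conclusion.** No change to the plan is called for. The label item is ambiguous in form, but the 2 mg dose on saline vials and the blinding statements in the Précis and Sections 4.1, 4.4.15 and 8 favour a masked phrase. On that reading the label discloses nothing. Measurement of the primary endpoint is sound on either reading, and the safety comparison by side is very probably sound.

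The conclusion assumes that the pharmacy prints the same text on both vials, as the dose line suggests, and that those judging adverse events are among the investigators covered by Section 4.4.15. If labels did show the real content and clinic staff saw them, attribution of one-sided events and evenness of delivery would be open to influence, by an amount the document gives no means to estimate. What remains is detail that a pharmacist and a study team resolve in their procedures: exact label text, who draws up, the irrigator's blind and the syringe wording. None of it alters an endpoint, an analysis or the sample size.

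### Section 4.4.12 contradicts itself on syringe size for fill volumes of 1 mL or more and states no loaded volume or stopping point for the 5-mL syringe

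*Protocol*

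**What the plan says.** Two paragraphs of Protocol section 4.4.12 describe how the treatment irrigation is prepared and given.

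The preparation paragraph applies to all subjects:
- Vial: "The dexamethasone vial will contain 2 mg of dexamethasone sodium phosphate for injection diluted with 0.9% sodium chloride for injection". The placebo vial is described only as 0.9% sodium chloride, with no quantity.
- Syringe: "Solution will be drawn from the vial into a 1 mL syringe".
- Volume: "The volume of each irrigation syringe will be determined by the parotid gland filling volume and specified in the medication order", followed by "The total volume will be between 0.5 and 1 mL".
- Label: the vial carries a dose of 2 mg and a volume.

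The administration paragraph splits subjects by fill volume:
- Below 1 mL: "the concentration of dexamethasone will be adjusted to administer a total dose of 2 mg", and "the dexamethasone or saline will be dispensed in a 1-mL syringe".
- 1 mL or more: "Dexamethasone (2 mg/mL) 1mL will be administered", and "a 5-mL syringe will be filled with the dexamethasone or saline solution before insertion". The syringe is then connected to the catheter and the contents are slowly instilled. The catheter stays in for 2 minutes, and suction collects what runs out.

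Two other sections bear on the point. Section 4.4.6 describes the screening fill-volume test: the syringe holds 1.5 mL of saline, injection stops at no more than 1 mL, and most subjects are expected to fall below 1 mL. Section 7.4 gives the dose as 2 mg on two occasions, 4 weeks apart.

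**The concern.** These are operating instructions for the study treatment, not background text. For a subject with a fill volume of 1 mL or more, the first paragraph calls for a 1 mL syringe and the second for a 5-mL one. The second paragraph keeps the 1 mL syringe for the other group, so the difference does not look like a slip in a single word.

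The 5-mL step also leaves out what the screening step supplies: the volume to load and the point at which to stop. Screening never tests a gland beyond 1 mL, so nothing is known about how these glands take a larger volume, and section 7.3 already lists duct trauma and perforation among the risks of irrigation.

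Two things are at stake. One is possible overfilling of a gland. The other is comparability: the primary analysis compares one gland with the other in the same subject, so a difference in instilled volume between glands or operators would be mixed with the drug effect.

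**Working it through.** **1. Reproduce the stated dose.** Dose = concentration × volume. For a fill volume of 1 mL or more, 2 mg/mL × 1 mL = 2 mg. This equals the vial content and label dose in section 4.4.12 and the dose in section 7.4. For smaller fill volumes the concentration is adjusted to keep 2 mg: at 0.5 mL it is 2 / 0.5 = 4 mg/mL, and at 0.75 mL it is 2 / 0.75 = 2.67 mg/mL. The dose statements agree throughout.

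**2. Set the two paragraphs side by side for a fill volume of 1 mL or more.**

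| Item | Preparation paragraph | Administration paragraph |
|---|---|---|
| Syringe | 1 mL | 5 mL |
| Volume loaded | set by fill volume in the medication order; total 0.5 to 1 mL | not stated; the syringe is to be filled |
| Dexamethasone available | 2 mg per vial | not stated |
| Volume administered | at most 1 mL | 1 mL of dexamethasone; no figure for saline |
| Stopping point | none beyond the total volume | none beside the syringe step |

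The syringe row is a direct contradiction. The loaded-volume row becomes one only if the 5-mL syringe is filled beyond 1 mL.

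**3. Test whether a literally filled 5-mL syringe fits the other figures.** Assume one vial per gland per irrigation, as the 2 mg label implies.
- Keep 2 mg/mL: 5 mL × 2 mg/mL = 10 mg, which is 10 / 2 = 5 vials. One vial cannot supply it.
- Keep one 2 mg vial and make it up to 5 mL: 2 / 5 = 0.4 mg/mL. Giving 1 mL then delivers 0.4 mg, which contradicts both the concentration and the dose.
- Keep one vial at 2 mg/mL: 2 mg / 2 mg/mL = 1 mL of solution, so the 5-mL syringe is not full.

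In each case a full 5 mL also exceeds the 0.5 to 1 mL total volume. No reading satisfies the filled 5-mL syringe, the vial content, the concentration and the volume limit at once.

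**4. Check the saline side.** The 2 mg content limits what can be loaded on the dexamethasone side. The placebo vial has no stated quantity, and the administration paragraph gives no saline volume for this group. Only the preparation paragraph's total volume and the medication order limit the saline volume, and that is the paragraph which the 5-mL instruction contradicts.

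**5. Compare with screening.** Section 4.4.6 loads 1.5 mL and stops at 1 mL, so loading more than is injected is not in itself an error. There, both numbers are written down; in the 5-mL treatment step, neither is.

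**The case against.** The strongest reply is that nothing in the protocol tells anyone to give more than 1 mL or 2 mg. The dose is the same wherever it appears, and for exactly this group the administered volume is stated as 1 mL. The volume is also to be written in the medication order and on the label, so an operator need not infer it from the barrel. A 5-mL barrel is a container size, and *filled with* can name the contents rather than the level. Most of this stands, and it limits the point to syringe size, loaded volume and stopping point.

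A reader might multiply 5 mL by 2 mg/mL and infer that five times the stated dose, 10 mg, could be given. The documents do not support that. It needs the syringe filled to capacity, the full concentration throughout and five vials' worth of drug, whereas the vial holds 2 mg and the text states 1 mL.

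It can also be said that the 5-mL sentence covers dexamethasone and saline alike, so the syringe by itself favours neither gland. That is correct. A difference between glands would need different volumes to be instilled. That remains possible because the dexamethasone vial has a stated content and the placebo vial has none, but the protocol does not show that it would happen.

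None of this makes the two paragraphs agree on the syringe, or supplies the missing loaded volume and stopping point.

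**Conclusion.** The point holds as an inconsistency in the instructions, not as a contradictory dose. For fill volumes of 1 mL or more, section 4.4.12 names two different syringes and leaves the loaded volume and stopping point of the 5-mL one unstated. A literal fill cannot be reconciled with the 2 mg vial, the 2 mg/mL concentration and the 1 mL limit together. The stated dose of 2 mg is consistent in sections 4.4.12 and 7.4.

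The reach is small. On section 4.4.6's expectation, it concerns fewer than half of the 16 subjects to be treated; the actual share is not given. No effect on the treatment estimate can be calculated, because the protocol gives neither that share nor any instilled volume under the 5-mL instruction. The possible consequences, overfilling of a gland or unequal volumes between glands or operators, depend on how the sentence is read in the clinic and on whether the medication order catches it. The conclusion assumes one vial per gland per irrigation. It takes no view on which instruction is right.

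**What to change.** Reconcile the two paragraphs of section 4.4.12, and the medication order with them, so that syringe, loaded volume, vial content and administered volume agree for every fill volume. State the loaded volume and the stopping point for the group with a fill volume of 1 mL or more, as section 4.4.6 does for screening. Do this for saline as well as dexamethasone, including the quantity in the placebo vial. The sponsor decides which text stands.

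The cost is a wording correction in one section and the matching pharmacy order. The design, sample size and analysis do not change.

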#### 4.4.13 **Description of blood collected solely for research**

Blood will be collected at Day 0 and Day 28 and Day 56, 24 mL total, to be used for future studies. The serum and peripheral blood mononuclear cells will be isolated and stored under appropriate conditions.

To determine the molecular mechanism of action of dexamethasone in this study, the following investigations are planned:

- Characterization of the fluid secretion mechanism after irrigation with corticosteroids, through assays of activities at the following levels: single protein (single-channel recording); subcellular; cellular (monitoring organellar and single-cell current, Ca2+, and pH); and tissue (use of volume changes as reported of fluid secretion by acinar cells and the micro-dissected sealed-duct system to measure all ductal secretory and signaling functions). Immunofluorescence will also be used to assay localization and expression levels of all key acinar and ductal transporters.
- Identification of changes in proteins involved in calcium signaling, such as Stim1. In vitro and in vivo studies with salivary gland cell lines and primary cells will be run in parallel to examine the effect of dexamethasone on the epithelial cells.
- 3. Exosomal microRNA biomarkers of inflammation. Saliva collected during the study will be used for isolation of exosomes, and the nucleic acid content of the exosomes will be correlated with the inflammatory status of the glands. Real-time quantitative polymerase chain reaction assays, microRNA microarrays, and/or deep sequencing will be used for identifying microRNAs.

# 4.4.14 Safety Follow-up

All subjects will be contacted by telephone for a Safety Follow-up, approximately 15 (±5) days after the last on-treatment visit (Day 56 Visit). A clinic visit may be conducted if deemed medically necessary or at the subject's request. Routine laboratory tests will be drawn only if clinically indicated. This contact will complete subject participation in the study.

# 4.4.15 End of Participation

During the study, subjects will continue receiving regular medical care from their primary physicians. The investigators will follow any AEs reported. Following completion of the study, subjects will continue medical care with their primary physicians. Results of technetium scans, MRIs, core needle biopsies, and laboratory tests will be provided to the subjects and/or their primary care physicians upon request. Subjects will be notified of their parotid gland treatment assignment only after data analysis has been completed and the investigators have been unblinded.

# 5 STORAGE OF DATA AND SAMPLES

# 5.1 Data

Study staff will complete electronic case report forms (eCRFs) via a web-based electronic data capture (EDC) system that is compliant with Part 11 Title 21 of the Code of Federal Regulations. The investigators will retain all study-related records for at least 2 years after discontinuation of the study.

